9.1. Description of some research procedures

9.1.1. Anamnesis

Collection of the anamnesis of the studied disease will be carried out during the screening, as well as information on significant past or current concomitant diseases (for example, allergic reactions, congenital and acquired heart and vascular diseases, other serious diseases, organ transplantation, mental disorders).

9.1.2. Collection of information about concomitant and previous therapy

All medications taken within 30 days prior to screening must be registered in the primary documentation. Separately, it will be clarified whether the patient took any prohibited drugs that prevent his/her inclusion in the trial.

9.1.3. Physical examination

Physical examination should be performed by the research physician. It includes (at a minimum) assessment of the patient's general condition and the following body systems: lymph nodes, mouth, and pharynx, lungs, cardiovascular system, abdominal cavity, extremities, musculoskeletal system, nervous system, and skin.

All changes considered clinically significant should be reported as an anamnesis before the study drug administration, and after the patient received the study drug, all changes should be reported as adverse events.

9.1.4. Vital signs

Vital signs include blood pressure (BP), heart rate (HR), and respiratory rate (RR), which must be measured and recorded by the staff of the research center.

Measurements of blood pressure and heart rate should be taken at the same body position throughout the trial.

9.1.5. Electrocardiography

Electrocardiography (ECG) is performed in accordance with normal clinical practice. A prerequisite is the registration of all 12 standard leads.

ECG interpretation is performed by an authorized researcher. It is necessary to indicate the date of ECG registration and provide a general conclusion. ECG records should be kept in the patient's medical records.

9.1.6. Complete and biochemical blood analysis

The tests are carried out in accordance with the methodology adopted in the clinical center laboratory. The following parameters will be measured:

- complete blood count (number of red blood cells, white blood cells, platelets, hemoglobin, hematocrit, leukocyte formula, ESR)
- biochemical blood parameters (glucose, ALT, AST, bilirubin, creatinine, total protein, sodium, potassium, CK, urea, cholesterol, HDL-C, triglycerides)
- coagulogram (fibrinogen, INR, APTT, prothrombin index)

In the case of clinically significant abnormalities, these phenomena are recorded as a concomitant disease (during the screening) or as an adverse event (during the trial).

9.1.7. Common urine analysis

To perform the analysis, approximately 50 ml of the first-morning portion of urine is taken, and the analysis is carried out according to local practice. The following parameters are measured:

- General characteristics (color, transparency, pH, density, protein, glucose, bilirubin/urobilinogen).
- Microscopy of urinary sediment (red blood cells, white blood cells, epithelium, cylinders, bacteria, salts).

In the case of clinically significant abnormalities, these phenomena are recorded as a concomitant disease (during the screening) or as an adverse event (during the trial).

10. THERAPY DURING THE TRIAL

Study drug: Fortelyzin®

Manufacturer: Supergene, LLC, Russia

Drug description

Pharmaceutical form: lyophilizate for preparation of a solution for intravenous administration, supplied with a solvent

Detailed description:

Lyophilizate: tablet-like freeze-dried mass of white or almost white color.

Solvent: colorless transparent liquid.

Reconstituted solution: colorless, transparent or slightly opalescent liquid.

Composition:

Active substance: Forteplase® (recombinant protein containing the amino acid sequence of staphylokinase) 5 mg (745,000 IU).

Excipients: L-arginine - 15,0 mg, L-histidine - 2,0 mg, glycine - 30,0 mg, povidone - 17:20,0 mg, polysorbate -20:0,4 mg.

Solvent: 5mL ampule of sodium chloride 0.9% solution for injection

Dosage regimen: Fortelyzin® will be assigned at a dose of 10 mg (1,490,000 IU).

Route of administration: intravenously in the form of a single bolus injection for 5-10 sec. The solution of Fortelyzin® is prepared immediately before administration: the content of a 5 mg vial (745,000 IU) is diluted in 5 ml of 0.9% sodium chloride solution. Non-storable!

Labeling: «Product for clinical trial only».

Active Comparator: Actilyse®

Manufacturer: Boehringer Ingelheim Pharma GmbH & Co. KG

Drug description

Pharmaceutical form: lyophilizate for preparation of a solution for infusion supplied with a solvent.

Detailed description:

Lyophilizate: freeze-dried mass of white or light yellow color.

Solvent: colorless transparent liquid

Composition:

Active substance: Alteplase 50,0 mg

Excipients: L-arginine: 1742.0 mg,

Phosphoric acid, 85 %: up to pH 7.2 ± 0.2,

Polysorbate 80: 3.5-5.0 mg.

Note

The excess is 3.5 % of the nominal amount of the active ingredient and excipients in the vial.

Residual traces: gentamicin (used in the production process).

Each vial of solvent contains:

Water for injection: 50 ml

1 ml of the solution after dilution contains 1 mg of alteplase.

Dosage regimen:

Actilyse ® is administered in accordance with the instructions for use in ischemic stroke at a dose of 0.9 mg/kg, maximum 90 mg, if a patient's weight exceeds 55 kg:

- 10% of the dose is administered intravenously via a syringe for one minute (bolus);
- the main dose of the drug (90% of the dose) is administered within 60 minutes (using a syringe dispenser / infusomat);

- during the infusion of the main dose, it is allowed to stop and continue the administration of Actilyse®, but the total duration of drug administration cannot exceed one hour after bolus (10% of the dose).
- Labeling: «Product for clinical trial only».

Previous treatment

Every effort should be made to find out what treatment the patient received within 30 days before administration of the study drug. The names of the drugs, the start and end dates of their use should be registered in the CRF.

Permitted concomitant therapy

In the first 24 hours after thrombolysis, the use of drugs to lower blood pressure is allowed: angiotensin-converting enzyme inhibitors and angiotensin receptor antagonists. If blood pressure drops during thrombolysis, the use of vasopressors (dobutamine, dopamine, and norepinephrine) is allowed.

In the case of allergic reactions during thrombolysis, the use of glucocorticoids and antihistamines is allowed.

If severe bleeding (especially from non-compressible vessels) occurs, the thrombolytic should be stopped and administration of fresh frozen plasma or fresh blood should be performed.

After 24 hours after thrombolysis, the use of antiplatelet agents – ASA, clopidogrel, ticlopidine, ticagrelor, anticoagulants: unfractionated or low-molecular-weight heparin, warfarin, dabigatran, bivalirudin, apixaban, rivaroxaban, fondaparinux is allowed. These drugs are permitted after thrombolysis only after CT/MRI examination to exclude intracranial hemorrhages (symptomatic and asymptomatic) and hematomas (Clinical recommendations for thrombolytic therapy in ischemic stroke, 2015).

In the absence of hemorrhagic transformation, the use of ASA is allowed during the entire follow-up period (90 days) after thrombolysis.

Prohibited concomitant therapy

In this trial, the use of antiplatelet agents (ASA, clopidogrel, ticagrelor, ticlopidine), anticoagulants (NPH, NMG, fondaparinux), oral anticoagulants (phenylin, syncumar), vitamin K inhibitor (warfarin), direct inhibitors of thrombin and blood clotting Factor X (dabigatran, bivalirudin, apixaban, rivaroxaban), glycoprotein IIb/IIIa receptor blockers, drugs that affect the rheological properties of blood (agapurin, vincocetine) is prohibited within 24 hours after thrombolysis.

11. EFFICACY ASSESSMENT

This trial involves a comparison group. Evidence of Fortelyzin® efficacy will be compared with the results of the application of Actilyse®.

Criteria for the efficacy evaluation of thrombolytic therapy

- The primary efficacy endpoint is a good functional recovery on day 90 (modified Rankin scale (mRS), 0-1 score).
- Secondary combined efficacy endpoint on day 90 – mRS (0-1) + NIHSS (0-1 score) + Barthel Index (BI) - 95 points or higher.
- Additional efficacy criterion – NIHSS score after 24 hours and after 90 days.

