The safety and efficacy of systemic thrombolysis therapy using Actilyse® in patients with ischemic stroke have been proven in a number of large randomized placebo-controlled clinical trials (NINDS, ECASS I, II, III, ATLANTIS), as well as the SITS-MOST and SITS-ISTR registers.

In addition, a high frequency of hemorrhagic transformation (6-23.8%) and a high 3-month mortality rate (18.2%) were noted in some studies with alteplase, which, according to the researchers, is associated with an initially high neurological deficit.

In this regard, the search for new thrombolytic drugs that can improve the efficacy and safety of thrombolytic therapy is an important scientific and economic task.

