7.4. Criteria for early termination of trial participants

A patient should be withdrawn from the trial immediately after any of the following situations occur:

- a patient or his/her legal representative or attending physician sends a request to exclude the patient from the trial, based on the withdrawal of Informed Consent (the patient's unwillingness to continue participation in the trial);
- pregnancy;
- significant violation of the Protocol procedures;

The reason for each unscheduled termination should be noted in the Case Report Form (CRF) in the section "Trial Completion". Follow-up will be performed for all patients who have dropped out of the trial due to adverse events or other safety parameters.

Follow-up will also be performed for all patients who have dropped out of the trial for other reasons, but also experience adverse events or have other safety parameters that might lead to discontinuation of therapy. In the case of early termination, the treatment of the underlying disease continues in accordance with recommendations and health standards.

Follow-up should be continued until the patient's condition is restored; until the diagnosis of an adverse event or a change in the safety parameter is stabilized or established chronically; as long as there are clinical indications for follow-up, or the duration of follow-up is determined by an attending physician-investigator.

In the case of pregnancy, every effort should be made to fully monitor the course of pregnancy until the moment of delivery, and child growth.

Randomized patients who did not complete the trial for reasons including those related to the trial drug will be included in the analysis of efficacy and safety data. Replacement of the removed randomized patients with newly included ones is not provided.

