12. SAFETY ASSESSMENT

- Safety endpoint - overall mortality on day 90.
- Safety endpoint - hemorrhagic transformation (all cases).
- Safety endpoint - symptomatic hemorrhagic transformation (as defined by ECASS III).
- The number of SAE and AE by organs and systems.

The assessment of safety is based on the number and severity of adverse events that may occur in the course of the trial. The drug is considered as well tolerated if no severe adverse events are registered during the trial (fatal outcome or life-threatening conditions of the patient), which, according to the Investigator, may be associated with the application of the drug studied.

Adverse events

Adverse event (AE) is any unfavorable medical occurrence in a patient or clinical trial subject administered a pharmaceutical product, which may not have a causal relationship with its use. Thus, an adverse event can be any adverse symptom (including deviation of the laboratory value from the norm), a complaint, or a disease, the time of occurrence of which does not exclude a causal relationship with the use of the medicinal product, regardless of the presence or absence of such communication.

Information about adverse events should be collected at each visit by interviewing the patient, as well as during physical examination and evaluation of laboratory and instrumental data. All adverse events that occur during the trial should be evaluated and documented.

When registering an adverse event, the following information should be reflected, if possible:

- the exact time of AE occurrence и разрешения
- the nature of the adverse event
- severity (mild, moderate, severe)
- causal relationship with the study drug
- whether the adverse event is serious
- actions taken (whether AE required any therapeutic measures)
- outcome

Adverse Event Grading:

- **Mild:** the presence of signs or symptoms that do not affect daily activities.
- **Moderate:** event has sufficient intensity to interfere with daily activities.
- **Severe:** inability to work or perform daily activities.

The connection between the development of an adverse event and the use of the study drug is determined by the WHO scale:

- **Certain:** Clinical manifestations of unforeseen adverse reaction (UAR), laboratory findings deviations that occur during the period of drug administration, can not be explained by the presence of existing diseases and the influence of other factors.

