18. STATISTICAL ANALYSIS OF RESEARCH MATERIALS

For Statistical Analysis R 3.5.1 package will be used.

Normally distributed variables will be described as mean (SD), ordinal variables as median (IQR), and categorical variables as number and percentage per category. For calculation of significant differences between proportions, we shall use the χ^2 method and for medians the Mann-Whitney U test (with a two-sided 5% level of significance). Ninety-five percent confidence intervals will be calculated for quantitative data.

The primary outcome and other continuous variables will be analyzed with a linear regression model. Binary variables will be tested using logistic regression models adjusted for the same stratification variables, p-values for the difference between treatment groups will be extracted from these models.

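### No value or rank is set for day-90 NIHSS in patients who have died; tested on observed scores alone, the comparison is among survivors and can favour the arm with more deaths

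*Combined protocol and SAP*

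**What the plan says.** - Section 11 (and the protocol summary) lists "NIHSS score after 24 hours and after 90 days" as an additional efficacy criterion. It stands below the primary endpoint (mRS 0–1 at day 90) and the combined secondary endpoint.
- Section 18 summarises "ordinal variables as median (IQR") and uses, "for medians the Mann-Whitney U test (with a two-sided 5% level of significance"). It also says: "The primary outcome and other continuous variables will be analyzed with a linear regression model". NIHSS is not named under either method. As NIHSS is an ordinal score, Mann-Whitney is the natural reading.
- Section 7.4 says that randomised patients who did not complete the trial "will be included in the analysis of efficacy and safety data". It gives them no value, and does not say whether the sentence is meant to cover deaths.
- Section 12 counts death on its own: "Safety endpoint - overall mortality on day 90".
- Section 1 mentions "a high 3-month mortality rate (18.2" per cent) in some alteplase studies, which their researchers linked to a high initial deficit.

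No section contains a missing-data rule, or a score or rank for a patient who died before an NIHSS assessment.

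**The concern.** A patient who has died has no day-90 NIHSS. Section 7.4 promises to include non-completers, but for this criterion the promise cannot be carried out without a rule. An analyst who applies the Section 18 test to the scores in the database will compare survivors, a group formed after randomisation.

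If one drug leads to more deaths, and those deaths are mainly among severe patients, that arm's surviving patients have lower scores. An efficacy criterion could then point in the opposite direction to the mortality endpoint. The trial is open-label, so a rule chosen after the data are in could also be influenced by knowledge of the arms.

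**Working it through.** **1. The plan's own figure.** The documents give no figure for NIHSS. The only calculation is the sample size in Section 17, for the primary endpoint: 54.8% in both arms, margin 16%, two-sided 5%, power 80%.

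n = (1.9600 + 0.8416)² / 0.16² × (2 × 0.548 × 0.452) = 7.849 / 0.0256 × 0.4954 = 151.9, so 152 per arm.

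With 10% added: 152 × 1.1 = 167.2, so 168 per arm and 336 in total. This reproduces the plan. NIHSS plays no part in it, and nothing below changes it.

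**2. How many patients could lack a score.** At the 18.2% mortality mentioned in Section 1: 168 × 0.182 = 30.6, about 31 per arm. This is an illustration, because the plan states no expected mortality.

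**3. Effect on the test.** The documents give neither a day-90 NIHSS distribution nor mortality by arm, so these inputs are assumed:

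- 3,000 trials per scenario, 168 per arm.
- Latent severity Z is standard normal in both arms. The score is exp(1.0 + 1.1Z) − 0.8, rounded and held within 0–42. There is therefore no underlying NIHSS difference.
- The number of deaths per arm is binomial. Those who die have the highest values of Z plus noise, with noise SD 3.0 (weak link between severity and death), 1.0 (moderate) or 0.35 (strong).
- Mann-Whitney at two-sided 5%, run (a) on survivors and (b) on all 168 per arm with death scored 43, above the scale maximum of 42.

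Percentage of trials significantly favouring the arm with more deaths (in the equal-mortality row, one given arm):

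| Mortality | Survivors, weak | Survivors, moderate | Survivors, strong | Death ranked worst |
|---|---|---|---|---|
| 18.2% vs 18.2% | 2.9% | 4.6% | 7.2% | 1.2–1.7% |
| 23.2% vs 18.2% | 4% | 10% | 18% | 0.3–0.4% |
| 28.2% vs 18.2% | 7% | 19% | 36% | at most 0.1% |
| 20% vs 10% | 7% | 20% | 35% | at most 0.3% |

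A second simulation gave about 5–20% for the second row and 7–38% for the third, with at most 0.4% when death was ranked worst. Taken together, the ranges are 4–20%, 7–38% and 7–35%.

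**4. Direction.** At 28.2% vs 18.2%, the probability that a score in the arm with more deaths exceeds one in the other arm is 0.45–0.49 among survivors (apparent advantage). It is 0.52–0.54 with death ranked worst (disadvantage). At equal mortality it is 0.50 under both methods.

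**5. How to read the sizes.** The nominal rate in one direction is 2.5%, but the equal-mortality row already reaches 7.2% under the strong link. This is because the number of deaths varies by chance and the most severe patients in each arm are then removed. The fair comparator for 18% is therefore about 7%, not 2.5%. A check with death drawn patient by patient brings the equal-mortality rate back to nominal and lowers the upper ends, but leaves the direction unchanged.

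**The case against.** A reader might infer that the plan prescribes a survivors-only test. It does not. Section 7.4, the nearest text, includes non-completers in the efficacy analysis. Mann-Whitney for NIHSS is an inference too, since Section 18 also sends continuous variables to linear regression. Both objections stand. The defect is a missing rule, and linear regression on observed scores would leave the same gap.

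A reader might also take 18.2% as the mortality expected here. Section 1 reports it for some studies, calls it high and ties it to a high initial deficit. This trial excludes NIHSS above 25 and ischaemia over more than a third of the middle cerebral artery territory, and limits age to 80. The count of 31 per arm is therefore not a forecast.

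The bias has conditions: mortality must differ between arms, and the excess deaths must fall on severe patients. With a weak link and a 5-point difference, the 4% is little above the 2.9% seen at equal mortality.

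The consequence is also limited. NIHSS is an additional criterion outside the non-inferiority hypothesis. The two higher endpoints are binary, and a death naturally counts as not reaching them, although the documents do not say so. Day-90 mortality is reported, so the excess needed for the bias would be visible beside it.

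These arguments limit the size and reach of the point. They do not supply the missing rule.

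**Conclusion.** The point holds as a gap in the analysis rule for one additional criterion, essentially at day 90; few deaths are expected by 24 hours. If observed scores alone are tested, mortality differs and deaths follow severity, the comparison leans towards the arm with more deaths. The false-advantage rates of 4–20%, 7–38% and 7–35% depend on assumed score distributions, assumed mortality and the assumed severity–death link. The upper ends also carry the inflation described in the working. Given the conditions, the direction does not depend on those choices.

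A reader might infer that the primary non-inferiority conclusion is at risk. The documents do not support that, because its endpoint is binary and NIHSS does not enter it. What is at risk is a misleading supportive efficacy claim. The rule should be fixed before the data are analysed.

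**What to change.** In Section 18, with a cross-reference from Section 11:

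- Name Mann-Whitney as the test for NIHSS.
- State that a patient who dies before the day-90 assessment is ranked worse than any observed score. Apply the same rule at 24 hours for consistency.
- Present survivors' NIHSS as a descriptive or sensitivity analysis, labelled as such.

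This takes two or three sentences. Sample size, visits and data collection do not change. The protocol already treats death this way in Section 2, where the neurological scale used in the rabbit model gives death the worst grade.

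The cost is that the comparison then mixes death with neurological deficit, which the text should say. The rule covers deaths only; day-90 scores missing for other reasons need a sentence of their own.

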12. SAFETY ASSESSMENT

- Safety endpoint - overall mortality on day 90.
- Safety endpoint - hemorrhagic transformation (all cases).
- Safety endpoint - symptomatic hemorrhagic transformation (as defined by ECASS III).
- The number of SAE and AE by organs and systems.

The assessment of safety is based on the number and severity of adverse events that may occur in the course of the trial. The drug is considered as well tolerated if no severe adverse events are registered during the trial (fatal outcome or life-threatening conditions of the patient), which, according to the Investigator, may be associated with the application of the drug studied.

Adverse events

Adverse event (AE) is any unfavorable medical occurrence in a patient or clinical trial subject administered a pharmaceutical product, which may not have a causal relationship with its use. Thus, an adverse event can be any adverse symptom (including deviation of the laboratory value from the norm), a complaint, or a disease, the time of occurrence of which does not exclude a causal relationship with the use of the medicinal product, regardless of the presence or absence of such communication.

Information about adverse events should be collected at each visit by interviewing the patient, as well as during physical examination and evaluation of laboratory and instrumental data. All adverse events that occur during the trial should be evaluated and documented.

When registering an adverse event, the following information should be reflected, if possible:

- the exact time of AE occurrence и разрешения
- the nature of the adverse event
- severity (mild, moderate, severe)
- causal relationship with the study drug
- whether the adverse event is serious
- actions taken (whether AE required any therapeutic measures)
- outcome

Adverse Event Grading:

- **Mild:** the presence of signs or symptoms that do not affect daily activities.
- **Moderate:** event has sufficient intensity to interfere with daily activities.
- **Severe:** inability to work or perform daily activities.

The connection between the development of an adverse event and the use of the study drug is determined by the WHO scale:

- **Certain:** Clinical manifestations of unforeseen adverse reaction (UAR), laboratory findings deviations that occur during the period of drug administration, can not be explained by the presence of existing diseases and the influence of other factors.

Manifestations of UAR regress after the drug discontinuation and occur again after repeated administration.

- **Probable.** Clinical manifestations of UAR, laboratory findings deviations are associated with the time of drug administration, unlikely to be related to concomitant diseases or other factors, and which regress with drug withdrawal. Response to the drug re-challenge is unknown.
- **Possible.** Clinical manifestations of UAR, laboratory findings deviations associated with the time of drug administration, but they can be explained by the presence of concomitant diseases or other drug administration and the influence of chemical compounds. Information on drug withdrawal response is unclear.
- **Questionable.** Clinical manifestations of UAR, changes in laboratory findings occur in the absence of a clear temporal association with the product administration; other factors are present (medicinal products, diseases, chemicals), which may be the cause of their occurrence.
- **Unlikely.** Clinical manifestations of UAR, laboratory findings deviations related to UAR, are difficult to assess. Additional data are needed for assessment, or the data are currently being analyzed.
- **Unclassified.** Reports on suspected UAR cannot be assessed, due to insufficient information, or it is contradictory.

In the case of adverse events, the choice of measures (follow-up, non-drug or drug therapy, hospitalization, and/or prolongation of existing hospitalization) is made by the physician-investigator based on the patient's interests to create optimal conditions and provide the patient with needed medical care.

Patients are monitored in the center until the full completion of any adverse event that occurred during the trial, and in the case of the development of a chronic disease - until the condition is stabilized. Adverse events in the form of changes in laboratory findings are observed until the normalization of the values or until the diagnosis of the chronic disease that caused such changes.

Serious adverse event (SAE)

A serious adverse event (SAE) is defined as any adverse event (AE) that at any dose results in:

- * death and/or disability;
- * development of a life-threatening condition;
- * prolongation of existing hospitalization;
- * development of congenital anomalies or malignant tumors.

In addition, any severe bleedings will be considered as SAEs in this trial:

- "major bleeding" according to the TIMI classification
- "severe or life-threatening bleeding" according to the GUSTO classification
- symptomatic intracerebral hemorrhage (SICH) was defined as any hemorrhage with neurologic deterioration, as indicated by an NIHSS score for 4 points and more than its value at baseline or the lowest one at 7 days after thrombolysis or any hemorrhage leading to death and had been identified as a predominant cause of neurologic deterioration (definition ECASS III)

Adverse events that do not fall into these categories should not be regarded as serious.

Any SAE, regardless of the causal relationship with the drug under trial, must be reported to Roszdravnadzor no later than 24 hours after the Investigator became aware of the SAE.

All paragraphs in the appropriate SAE report form must be filled in. Information about the SAE should be included in the Case Report Form.

Bleedings

All bleeding events should be registered in the patient's CRF. Each bleeding is classified according to the GUSTO and TIMI scales. Bleeding that is classified according to TIMI as "major" or "severe or life-threatening" – according to the GUSTO scale are considered as SAE in this trial.

Safety assessment is carried out based on the number and severity of AEs and SAEs detected during the trial.

If a serious adverse event occurs, the Investigator must:

- provide (if necessary) appropriate qualified medical care, including laboratory and instrumental studies;
- inform Roszdravnadzor within 24 hours about the occurrence of SAE and send (fax, e-mail) a Report form on a serious adverse event;
- indicate all adverse events in the patient's CRF;
- continue to monitor the patient's condition until the SAE is fully completed.

In addition, if there is major or moderate bleeding, its localization is indicated:

- gastrointestinal tract;
- urogenital tract;
- retroperitoneal space;
- central nervous system;
- parenchymal organs.

In minor bleeding occurs, the immediate cause of its occurrence and/or localization is indicated:

- puncture;
- damage to blood vessels;
- bleeding from the gums.

